### **9.7.5 Evaluability of patients for analysis**

All main descriptions and analyses of safety and efficacy data will be based on the Full Analysis Set, as defined in ICH E9 Guidelines (Statistical Principles for Clinical Trials). The Full Analysis Set includes all dosed patients with data after dosing, except those patients who has had received a positive inhibitor test result after inclusion in the study for a test performed prior to first dose of turoctocog alfa, these patients will be listed separately.

No formal Per-Protocol analysis is planned. However, the sensibility of the results with respect to single patient's data may be investigated by performing additional analyses on subsets of data.

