#### 8.2.2 Secondary endpoints

##### Safety endpoints

- Number of adverse reactions (ARs) reported during the study period
- Number of serious adverse reactions (SARs) reported during the study period

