**Table 9–2 Recommended laboratory scheme for FVIII inhibitors and recovery**

	0 EDs	10-15 EDs	50-75 EDs	~100 EDs
FVIII inhibitors	X 	X 	X 	X 
FVIII recovery	X	X	X	X

A 48 hours washout period is recommended

[figure not shown]
In the event that a patient has a positive inhibitor test obtained within 4 weeks prior to first dose of turoctocog alfa, the patient cannot be included in the study according to inclusion criteria no. 5, see section [9.2.2](#). In the event that a patient has a positive inhibitor test result after inclusion in the study for a test performed prior to first dose of turoctocog alfa, the patient may proceed in the study but will not be included in the full analysis set. In the event that a patient has a positive inhibitor test ( $\geq 0.6$  BU for central laboratory analyses, or above the specific local laboratory reference range) after inclusion and dosing in the study, the patient should visit the clinic again according to local practice (recommended to be performed as soon as possible - preferably within 2 weeks) to take a confirmatory inhibitor test on a separately drawn sample. The confirmatory sample should preferably be taken prior to any change of treatment. Even if the second inhibitor test is positive, the patient may continue in this study.

If this is decided, dosing, dosing frequency and more frequent visits for inhibitor sampling, if applicable, will be decided by the Physician based on the clinical evaluation. If a patient is to be withdrawn due to a confirmed inhibitor test, the Physician is encouraged to schedule an End of study visit (Visit 3) according to local clinical practice, and preferably within 1 month.

A positive inhibitor test should be reported as an AESI, see section [11.3](#). If the presence of inhibitors is confirmed by a second test this should be reported as a serious adverse reaction (SAR), see section [11.3](#). If the second inhibitor test is negative this should be reported as a follow-up to the reported AESI, see section [11.4](#). When lack of therapeutic effect is indicated by bleeding or laboratory findings, the Physician is encouraged to sample for FVIII inhibitor detection.

It is recommended that the Physician should upon a clinical suspicion of inhibitor development perform a FVIII inhibitor test.

The recommended process of inhibitor testing in case of a positive inhibitor test during the study is outlined in [Figure 9–1](#).

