#### **9.7.4 Secondary endpoints**

##### **Safety endpoints**

- Number of adverse reactions (ARs) reported during the study period
- Number of serious adverse reactions (SARs) reported during the study period

ARs and SARs reported during the study will be summarised by number of reactions and number of patients with any reaction. Since patients will have different durations in the study adverse reaction rates (reactions per 100 patient years of exposure) will also be calculated and presented. Similar summaries cross-classified by severity will also be made. The summary tables will be made by type of regimen.

Furthermore, listings will be provided displaying all ARs and SARs reported during the study including pertinent clinical information.

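### The set used for the main safety summaries leaves out exposed, followed patients whose pre-dose inhibitor test is reported positive after inclusion, so their reactions are listed but not counted

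*Protocol*

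**What the plan says.** Section 9.7.5 names one analysis set for safety and efficacy alike: "All main descriptions and analyses of safety and efficacy data will be based on the Full Analysis Set". Membership is defined as follows: "The Full Analysis Set includes all dosed patients with data after dosing, except those patients who has had received a positive inhibitor test result". The exception covers a result that arrives once the patient is already enrolled, on a sample drawn before any turoctocog alfa was given; such patients go to a separate listing.

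Section 9.3.3.5, in the text after Table 9–2, confirms what happens to such a patient: "the patient may proceed in the study but will not be included in the full analysis set". Section 9.3.3.1 sets the period of AR monitoring as first exposure to turoctocog alfa until the last visit, with no exception for these patients.

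The safety endpoints in section 8.2.2 are the numbers of ARs and SARs; the second reads "Number of serious adverse reactions (SARs) reported during the study period". Section 9.7.4 plans the summaries: "ARs and SARs reported during the study will be summarised by number of reactions and number of patients with any reaction", and "adverse reaction rates (reactions per 100 patient years of exposure) will also be calculated and presented". It also promises listings of every AR and SAR reported. Section 9.7.3 makes the same exclusion separately, in both the numerator and the denominator of the primary inhibitor endpoint.

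**The concern.** An inhibitor already present before the first dose did not arise on turoctocog alfa, so leaving it out of an incidence estimate is right. That argument does not carry over to an allergic reaction, or any other suspected reaction, that happens after the patient has been given the product. Such a patient has been exposed and followed and has contributed safety data.

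Because section 9.7.3 already contains its own exclusion, repeating it in the Full Analysis Set does nothing for the primary endpoint. Its practical effect is to remove these patients from the main AR and SAR summaries, and from efficacy. In a post-authorisation safety study whose safety endpoints are counts of reported reactions, the headline counts could then be smaller than the number of reactions actually reported. The rates would also describe a subset of exposed patients chosen by a laboratory result.

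**Working it through.** The protocol gives no expected number of excluded patients and no expected AR rate, so there is no stated figure to reproduce. The check is mainly a trace of who is in which output.

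**Trace of one patient.** Take a patient who enrols, has a sample drawn before the first dose, is dosed, and whose result then comes back positive.

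| Question | Section | Answer |
|---|---|---|
| May the patient stay in the study? | 9.3.3.5 | Yes |
| Are ARs collected? | 9.3.3.1 | Yes, first exposure to last visit |
| In the primary inhibitor endpoint? | 9.7.3 | No, excluded there explicitly |
| In the Full Analysis Set? | 9.3.3.5, 9.7.5 | No |
| In the main AR/SAR counts and rates? | 9.7.4 with 9.7.5 | No, both events and exposure time drop out |
| In listings? | 9.7.4, 9.7.5 | Yes |
| In any other named safety set? | 9.7.5 | None is defined; the optional extra analyses are on subsets of the data |

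The endpoint definition in 8.2.2 would count this patient's reactions. The analysis set in 9.7.5 would not.

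**Size per patient.** Section 9.2.1 plans about 70 patients included. Share removed = k/N, where k is the number excluded: 1/70 = 1.4%, 2/70 = 2.9%, 3/70 = 4.3%.

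**Illustration, with assumed inputs.** Let N = 70 exposed, k = 1 to 3 excluded, p = share of Full Analysis Set patients with an AR (5% or 10%), and q = share of excluded patients with an AR (from p up to 100%). None of k, p or q is in the protocol.

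Percentage with an AR among all exposed = [(N − k)p + kq] / N.

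- q = p: unchanged, 5.0% or 10.0%.
- p = 10%, q = 100%, k = 1: (6.9 + 1)/70 = 11.3%. With k = 3: (6.7 + 3)/70 = 13.9%.
- p = 5%, q = 100%, k = 1: (3.45 + 1)/70 = 6.4%. With k = 3: (3.35 + 3)/70 = 9.1%.

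Share of patients with an AR who are missing from the main count = kq / [(N − k)p + kq].

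- q = p: k/N, that is 1.4% to 4.3%.
- q = 100%: from 1/7.9 = 12.7% (p = 10%, k = 1) to 3/6.35 = 47.2% (p = 5%, k = 3).

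So percentages do not move if the excluded patients react like the rest. They move noticeably only if those patients react much more often. The counts are incomplete whenever any excluded patient has a reaction.

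**The case against.** The best defence has four parts.

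- **The events are not lost.** Section 9.7.4 lists all ARs and SARs without restricting the set, section 9.7.5 lists the excluded patients separately, and it restricts only the main analyses. Safety reporting under section 11 does not depend on the Full Analysis Set. This stands. A reader might infer that such reactions vanish from the report, or that every safety output is affected; the text does not support either. A listing, however, is not a count or a rate, and no other safety summary is specified.
- **The group should be very small.** Inclusion criterion 5 in section 9.2.2 requires a negative test within four weeks before first dose. For patients already on the product at inclusion, section 9.3.3.5 requires the pre-treatment result to be available and negative. The exclusion arises mainly when someone enrols before the first dose and a further pre-dose sample later proves positive. This also stands, and it limits the weight of the point.
- **The exclusion has some logic.** These patients turn out not to be clearly inhibitor-free at first dose, which is the state the criterion is meant to secure. That is a fair argument for the inhibitor endpoint and for efficacy. The protocol does not make it for other reactions.
- **The excluded patients need not be different.** It is tempting to say that they carry an unrecognised inhibitor and so will react differently. Section 9.3.3.5 calls an inhibitor confirmed only after two consecutive positive tests, whereas one positive result triggers the exclusion. A different safety experience is possible but not shown.

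A reader might also object to the condition that patients need data after dosing. That condition hides no reaction, because a reported AR is itself data after dosing.

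**Conclusion.** The concern holds for the main AR and SAR counts and rates. As written, an exposed and followed patient with a late-reported positive pre-dose test contributes neither events nor exposure time to them, although the endpoints cover reactions reported during the study without that restriction. No reason is given for carrying the exclusion beyond the inhibitor endpoint.

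The likely size is small: about 1.4% of 70 patients for each one excluded, with the number of such patients unstated and probably low. Any larger effect rests on the assumed values above. One might also be tempted to express the effect as a change in an exact upper confidence limit for SARs, but the protocol plans that limit only for inhibitor incidence, so it would describe no planned output. The point is worth correcting because it is a selective exclusion in a safety study and is easy to remove.

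**What to change.** In section 9.7.5, define a Safety Analysis Set of all enrolled patients exposed to turoctocog alfa, with the AR window of section 9.3.3.1 (first exposure to last visit). Use it for the AR and SAR counts and rates in section 9.7.4. The set should not be limited to exposure after inclusion, because first exposure may come before inclusion and ARs are collected from that point.

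Keep the exclusion for the primary inhibitor endpoint in section 9.7.3 and for the Full Analysis Set used for efficacy. State that the inhibitor found in the pre-dose sample is not itself counted as a reaction to turoctocog alfa. In section 9.3.3.5, add that these patients remain in the Safety Analysis Set. The separate listing can stay.

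The cost is a wording change and one more analysis-set flag. The AR and SAR counts may become slightly less favourable. No new data, visits or change in patient care are needed.

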## **9.8 Quality control**

### **9.8.1 Monitoring procedures**

During the course of the study, the monitor should visit the study site at intervals specified in the monitoring guideline for the study. The purpose of these visits is to ensure that the protocol has been adhered to, that all issues and data have been recorded and to collect completed pCRF pages. The extent of source data verification and validation of endpoints will be described in the monitoring guideline for the study. The monitor must ensure that the pCRFs are completed and collected.

### 9.8.2 Critical documents

- Before the Physician starts the study (i.e. obtains informed consent from the first patient), the following documents must be available at Novo Nordisk:
- Regulatory approval and/or notification as required
- Curricula vitae of Physician (current, dated and signed and/or supported by an official regulatory document)
- Signed and dated agreement on the final protocol
- Signed and dated agreement on any substantial amendment(s), if applicable
- Approval/favourable opinion from IRB/IEC or another relevant scientific body according to local legislation clearly identifying the documents reviewed: the protocol, any substantial amendments, patient information/informed consent form and any other written information to be provided to the patient, patient enrolment procedures
- Copy of IRB/IEC or another relevant scientific body according to local legislation approved patient information/informed consent form/any other written information/advertisement
- Non-interventional study agreement

### 9.8.3 Retention of study documentation

Patient notes and records must be kept for the maximum period permitted by the hospital, institution or private practice.

Novo Nordisk will comply with all the requirements of GPP and relevant national legislation related to archiving of study documentation. Records containing patient sensitive data must not be archived by Novo Nordisk, but must be kept with the Physician and patient and according to local regulations pertaining to personal data protection.

The physician must agree to archive the documentation pertaining to the study in an archive for at least 5 years after final report/first publication of the study, whichever comes later. The Physician should not destroy any documents without prior permission from Novo Nordisk.

Novo Nordisk will retain the documentation pertaining to the study according to company procedures or in accordance with national regulations if they require a longer retention period.

### 9.8.4 Archiving of statistical programs

The programming plan is prepared with input from the Study Statistician using the Novo Nordisk's template. The programming plan is stored in the document sub-directory in the relevant study folder in the statistical computing environment. The final programs and outputs of a clinical study and all relevant documentations in form of specifications, data, programs, log files, output files, validation documentations and other documentation used in the process of reporting the study are saved in records. By saving all documentation used in the reporting process we are able to document when

and on which data, by which program(s) any given output is created. Furthermore, it will be possible at all times to regenerate all output, if necessary.

### **9.9 Limitations of the research methods**

As this is a non-interventional study potential confounding factors can not be ruled out. Data collection will reflect routine clinical practise rather than mandatory assessments at pre-specified time points, which may have an impact on the amount of data and its interpretation. Concerning the issue of bleeding episode evaluation of home treatment the risk of misclassification is relevant. Patients will receive and be asked to enter data (e.g. treatment and bleeds) in a diary. The Physician is encouraged to review the diary data together with the patient/caregiver during visits to the clinic.

### **9.10 Premature termination of the study**

The sponsor, Physician or a pertinent regulatory authority may decide to stop the study or part of the study at any time, but agreement on procedures to be followed must be obtained.

If a study is prematurely terminated or suspended, the Physician and/or sponsor should promptly inform the IEC/IRB or another relevant scientific body according to local legislation and provide a detailed written explanation. The pertinent regulatory authorities should be informed according to national regulations.

If after the termination of the study the risk/benefit analysis has changed, the new evaluation should be provided to the IEC/IRB or another relevant scientific body according to local legislation in case it will have an impact on the planned follow-up of the patients who have participated in the study. If so, the actions needed to protect the patients should be described.

### **9.11 Indemnity statement**

Novo Nordisk carries product liability for its products and liability assumed under the special laws, acts and/or guidelines for conducting clinical/non-interventional studies in any country, unless others have shown negligence.

Novo Nordisk assumes no liability in the event of negligence or any other liability by the clinics or doctors conducting experiments or by persons for whom the said clinic or doctors are responsible.

Novo Nordisk accepts liability in accordance with local laws and guidelines.

## 10 Protection of human subjects

The study will be conducted in accordance with Good Pharmacoepidemiology Practice (GPP), reference.

The only burden added to the patient's life by participating in this study is entering of data into a diary. A diary for home treatment is recommended or required by most hospitals and will thus serve a disease management purpose apart from the purpose of reporting to the study. In this study, patients will be provided with a diary. The potential benefits for the patient are the systematic assessments of safety, especially comprising FVIII inhibitors and lack of effect.

There are no risks associated with this study. It is thus evaluated that the benefits outweighs the extra burden with participating in this study.

### 10.1 Informed consent form for study patients

Informed consent from all study participants is required before any data is entered into the pCRF and/or any blood samples are sent to the Central Laboratory for analysis.

A voluntary, signed and personally dated informed consent form must be obtained from the patient and/or the patient's parent(s) or LAR prior to any study related activity.

In obtaining and documenting informed consent, the Physician must comply with the applicable regulatory requirement(s) and adhere to the requirements in the Declaration of Helsinki.

If a patient is under age, then the patient's assent must also be obtained according to local requirements.

The task of seeking informed consent can only be performed by the Physician or another medically qualified person delegated by the Physician, if permitted by local regulation, who must sign and date the patient information/informed consent form. If information becomes available that may be relevant to the patient's willingness to continue participating in the study, the Physician must inform the patient/parents and/or the patient's LAR in a timely manner and a revised written informed consent must be obtained.

Prior to any study-related activity, the Physician must give the patient and/or the patient's LAR oral and written information about the study in a form that the patient or the patient's LAR can read and understand. This includes the use of impartial witness where required. In this study the notion of legal representative should be understood as either parents, or LAR, as defined in Member States' national laws, who consents on behalf of the child.

Children, incapable of giving consent, are included as patients in this study in accordance with Health Authority guidelines for development of FVIII products.

**Consent:** As a child is unable to provide legally binding consent, informed consent must be obtained from the parents/LAR on the child's behalf. The specific and written informed consent of the parents/LAR must be sought prior to enrolling a child in the study. Information should be given by an experienced Physician to each parent, or the LAR, on the purpose of the study and its nature.

**Assent:** When a patient deemed legally incompetent, such as a child, is able to give assent to decisions about participation in the study, the Physician must offer the possibility for the child to give assent in addition to the consent of the parents/LAR. An "Assent form" will be provided and can be used when appropriate and when the child is capable of forming an opinion and assessing.

The requirement for obtaining informed consent from a patient's LAR is that the patient is unable to provide informed consent, and the process has been approved by the relevant IRB/IEC.

An informed consent form for the male patient's female partner must be signed before any data is collected from the patient's female partners i.e. in case of pregnancy.

### **FVIII genotype**

Patients/parents or LAR will be asked if available result(s) of previous FVIII genotype test(s) or result from a genotype test performed during the patient's participation in the study may be documented. If agreed to, this should be documented on a separate page in the Informed Consent form.

### **10.2 Data handling**

If the patient/parents or the patient's LAR withdraws the previously given informed consent the patient's data will be handled as follows:

Data collected will be used as part of the study population

Safety events will be reported to the department responsible for Global Safety, Novo Nordisk/regulatory authorities

If data is used, it must always be in accordance with local law and IRB/IEC procedures.

### **10.3 Institutional Review Boards/Independent Ethics Committee**

Before commencement of the study, the protocol, any amendments, patient information/informed consent form, any other written information to be provided to the patient, patient enrolment procedures, if any, the Physician's current CV and/or other documentation evidencing qualifications, and other documents as required by the local IRB/IEC or another relevant scientific body according to local legislation should be submitted. The submission letter should clearly identify (by study identification number, including version, title and/or date of the document) which documents have been submitted to the IRB/IEC. Written approval/favourable opinion must be

obtained from IRB/IEC or another relevant scientific body according to local legislation before commencement of the study.

During the study, the Physician must promptly in accordance with local requirements report the following to the IRB/IEC or another relevant scientific body according to local legislation: unexpected serious adverse reactions, amendments to the protocol according to local requirements, deviations to the protocol implemented to eliminate immediate hazards to the patients, new information that may affect adversely the safety of the patients or the conduct of the study (including new risk/benefit analysis in case it will have an impact on the planned follow-up of the patients), annually written summaries of the study status and other documents as required by the local IRB/IEC or another relevant scientific body according to local legislation.

Amendments must not be implemented before approval/favourable opinion, unless necessary to eliminate immediate hazards to the patients.

The Physician must maintain an accurate and complete record of all submissions made to the IRB/IEC or another relevant scientific body according to local legislation. The records should be filed in the Physician's study file and copies must be sent to Novo Nordisk.

